3.1.2 Study Procedures for All Cohorts

Patients will be required to provide sample tumor tissue showing the presence of CIS, to be obtained within 60 days prior to study entry. Tissue should be submitted as formalin-fixed paraffin-embedded (FFPE) blocks (blocks preferred) or at least 10 unstained slides, with an associated pathology report, for central testing. Patients with fewer than 10 unstained slides available at baseline (but no fewer than five) may be eligible following discussion with the Medical Monitor. The Sponsor may replace patients who are later found to be unevaluable for tumor PD-L1 expression by central testing.

Tumor response assessment via cystoscopy and urine cytology will occur every 12 weeks for the first 2 years, and every 24 weeks thereafter until 5 years, and then yearly.

A mandatory tissue biopsy will be obtained from all patients 6 months after C1D1 of atezolizumab. For patients in Cohort 1A, biopsies should be obtained up to 21 days prior to atezolizumab administration. For patients in Cohorts 1B, 2, and 3, biopsies should be obtained 14–21 days prior to BCG intravesical instillation (e.g., Weeks 10, 22, 46, 70 and 94; see [Appendix 3](#)).

The Sponsor may replace patients who are discontinued from the study before the required tumor biopsy samples are obtained.

At the 6-month timepoint (Week 24 visit), documentation of a complete response (CR) is required to continue on study treatment.

Definition of Complete Response (must meet all 3 criteria):

- Cytology: not positive (see below)
- Upper Urinary Tract Imaging (if performed): normal, or abnormal but supportive of CR (with non-positive selective ureteral cytologies)

- Cystoscopy: bladder appears normal; or bladder appears abnormal but all biopsies are negative; or any grade papilloma, any grade papillary urothelial neoplasm of low malignant potential (PUNLMP), or low grade pTa

Interpretation of Urine Cytology:

- If results are Unsatisfactory, Atypical Cell, Suspicious, or Indeterminate, then assay must be repeated no less than 24 hours and up to 21 days later.
- If the results are again Unsatisfactory or Atypical Cell (2 in a row), then treat as if the result was negative.
- Two consecutive Suspicious or Indeterminate urine cytology specimens require further evaluation by cystoscopy and/or upper tract imaging as deemed appropriate by the investigator

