There may be circumstances in which either BCG or atezolizumab is permanently discontinued, but it may still be possible to continue the remaining study treatment with approval of the Medical Monitor. Patients in Cohorts 1B, 2, or 3 (atezolizumab plus BCG) who discontinue atezolizumab after receiving fewer than three cycles may be replaced.

All patients will be closely monitored for serious adverse events or protocol-defined events of special interest for 90 days or 30 days for adverse events, following their last dose of study therapy (atezolizumab and/or BCG) or initiation of non-protocol anti-cancer therapy, whichever occurs first. Safety assessments will include the incidence, nature, and severity of adverse events, changes in selected vital signs and laboratory abnormalities graded per NCI CTCAE v4.0.

Serum and plasma samples will be collected to monitor atezolizumab pharmacokinetics and to detect the presence of antibodies to atezolizumab.

Patient samples, including archival tumor tissues, as well as plasma, whole blood, and urine will be collected for future exploratory biomarker assessments.

A treatment completion/discontinuation visit will be performed for all patients within 30 days after the last administration of study treatment.

[figure not shown]
Patients who discontinue study treatment for a reason other than disease recurrence/progression or cystectomy (e.g., because of toxicity) will continue to undergo tumor assessments per protocol until they experience disease recurrence/progression or cystectomy, until the patient dies, withdraws consent, or until the study closes, whichever occurs first, for a maximum of 5 years after enrollment.

In addition, all patients will be followed for survival and subsequent anti-cancer therapy beginning 6 months after the treatment completion/discontinuation until loss to follow-up, death, withdrawal of consent, or study termination by the Sponsor, whichever occurs first, for a maximum of 5 years after enrollment.

Figure 6 presents the treatment plans for each cohort. The schedules of assessments are provided in Appendix 1 and Appendix 2.

[figure not shown]
Figure 6 Treatment Plans

Cohort 1A

Cohort 1A: Patients receive atezolizumab 1200 mg IV q3w.

Cohort 1B

[figure not shown]

BCG = bacille Calmette-Guérin.

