3.5.4 Efficacy Outcome Measures

The primary efficacy outcome measure for this study is as follows:

- CR at the 6-month evaluations after the start of study treatment. Patients must be evaluated for CR by both cystoscopy and cytology and bladder biopsies will be required for the 6-month CR disease assessment.

The secondary efficacy outcome measures for this study are as follows:

- CR at the 3-month disease assessment, evaluated by both cystoscopy and cytology.
- Duration of CR, defined as time from first occurrence of a documented CR until the time of recurrence of NMIBC or death from any cause
- RFS rate at 6, 12, and 18 months, defined as the proportion of patients who are alive and free of persistent/recurrent high-risk NMIBC
- Bladder-intact DFS, defined as time from first study treatment to earliest evidence of progression to muscle-invasive disease in the bladder, regional pelvic progression, distant metastasis, bladder cancer–related death, or cystectomy or death from any cause
- PFS, defined as the time from first study treatment to the first occurrence of progression to muscle-invasive disease or death from any cause
- CFS, defined as the time from first study treatment to cystectomy or death from any cause
- Overall survival, defined as the time from first study treatment to death from any cause

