4.5.5 Tumor and Response Evaluations

Screening and tumor response assessment will be in accordance with national (EAU AUA, and NCCN) guidelines, which recommend cystoscopic examination and urine cytology every 12 weeks for the first 2 years, and every 24 weeks thereafter (or as clinically appropriate) until 5 years, and then yearly. Upper tract imaging with CT urography or intravenous pyelogram will be performed at the 6- and 18-month disease assessments. Annual upper tract imaging thereafter is recommended as clinically indicated.

Screening assessments must include imaging of the upper tract collecting system, which may include any one or more of the following: intravenous pyelogram, CT urography, renal ultrasound with retrograde pyelogram, ureteroscopy, or magnetic resonance imaging urogram. Pelvic CT before TURBT may be considered, but is not required.

Primary assessment of tumor (at screening and while on study) will be with cystoscopy and urine cytology.

White-light cystoscopy, narrow band imaging cystoscopy, or fluorescent (blue-light) cystoscopy will be acceptable for baseline assessment. The same methodology used to assess disease sites at screening should be used throughout the study except when medical contraindicated (e.g., the same cystoscopy protocol and urine examination).

The Sponsor may replace patients who have had a change in the type of cystoscopy (e.g., screening with white-light cystoscopy and follow-up evaluation with blue-light cystoscopy) to ensure consistent evaluation over time. All known sites of disease must be documented at screening and re-assessed at each subsequent tumor evaluation. A Bladder Map template ([Appendix 11](#)) has been provided and should be used to document the approximate size and location of abnormalities observed at screening, baseline, and on study cystoscopy/TURBT assessments.

Mandatory bladder biopsies will be performed at the 6-month tumor assessment. In absence of visible tumor, template biopsies should be obtained from all quadrants of the bladder. Template biopsies may be performed under anesthesia, at the discretion of the investigator. Regions of the template biopsies should include the trigone, left lateral wall, right lateral wall, posterior wall, and dome. Where feasible, the same evaluator should perform assessments if possible to ensure internal consistency across visits.

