4.5.11 Follow-Up Assessments

See the study flowchart provided in [Appendix 1](#) and [Appendix 2](#) for specified follow-up assessments.

Ongoing Tumor Assessments

Patients who discontinue study treatment for a reason other than disease recurrence/progression or cystectomy will continue to undergo tumor assessments per study protocol, until they experience disease recurrence/progression or cystectomy, until the patient dies, or withdraws consent, or until the study closes, whichever occurs first, for a maximum of 5 years after enrollment.

Patients who start a new anti-cancer therapy in the absence of disease recurrence/progression should continue to be followed for recurrence/progression according to the protocol schedule of response assessments unless consent is withdrawn or the patient experiences disease recurrence/progression or death or until study termination or withdrawal from study, whichever occurs first.

Adverse Events

See Sections [5.2–5.5](#) for information on reporting adverse events.

Survival and Subsequent Anti-Cancer Therapy Follow-Up

All patients will be followed for survival and subsequent anti-cancer therapy beginning 6 months after the treatment completion/discontinuation visit. Survival and subsequent anti-cancer therapy follow-up information will be collected via telephone calls, patient medical records, and/or clinic visits approximately every 6 months until loss to follow-up, death, withdrawal of consent, or study termination by the Sponsor, whichever occurs first, for a maximum of 5 years after enrollment. Request to withdraw from follow-up must be documented in the source documents and signed by the investigator. If the patient

withdraws from study treatment but not from follow-up, the study staff may use a public information source (e.g., county records) to obtain information about survival status only.

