- ^x Primary assessment of tumor will be with cystoscopy and urine cytology. Tumor response assessment will occur every 12 weeks for the first 2 years, and every 24 weeks thereafter (or as clinically appropriate) until 5 years, and then yearly. White-light cystoscopy, narrow band imaging cystoscopy, or fluorescent (blue-light) cystoscopy will be acceptable for baseline assessment. The same methodology used to assess disease sites at screening should be used throughout the study except when medically contraindicated (e.g., the same cystoscopy protocol and urine examination). All known sites of disease must be documented at screening and re-assessed at each subsequent tumor evaluation. Random biopsies must include all four quadrants of the bladder. The same evaluator should perform assessments if possible to ensure internal consistency across visits. The Bladder Map template ([Appendix 11](#)) should be used to document the approximate size and location of any abnormalities, as well as the approximate location of any biopsies performed. For all patients, additional evaluation (imaging, exam under anesthesia, biopsies) should be performed at investigator discretion for any of the following circumstances:

Appendix 1

Schedule of Assessments: Cohort 1A (cont.)

- Abnormal cystoscopy
 - Positive urine cytology
 - Two sequential suspicious/indeterminate urine cytology specimens
- ^y Patients who discontinue all study treatment for a reason other than disease recurrence/progression or cystectomy will continue to undergo tumor assessments every 6 months until they experience disease recurrence/progression or cystectomy, until the patient dies, or withdraws consent, or until the study closes, whichever occurs first, for a maximum of 5 years after enrollment.
- ^z Health-related quality of life will be assessed using the EORTC QLQ-C30 and EORTC QLQ-NMIBC24.
- ^{aa} Concomitant medications include any prescription medications or over-the-counter medications. At screening, any medications the patient has used within the 7 days prior to informed consent should be documented. At subsequent visits, changes to current medications or medications used since the last documentation of medications will be recorded.

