- ^y Primary assessment of tumor will be with cystoscopy and urine cytology. Tumor response assessment will occur every 12 weeks for the first 2 years, and every 24 weeks thereafter (or as clinically appropriate) until 5 years, and then yearly. Cystoscopy that falls prior to BCG should be performed at least 14 days prior to BCG administration. White-light cystoscopy, narrow band imaging cystoscopy, or fluorescent (blue-light) cystoscopy will be acceptable for baseline assessment. The same methodology used to assess disease sites at screening should be used throughout the study except when medically contraindicated (e.g., the same cystoscopy protocol and urine examination). All known sites of disease must be documented at screening and re-assessed at each subsequent tumor evaluation. Random biopsies must include all four quadrants of the bladder. The same evaluator should perform assessments if possible to ensure internal consistency across visits. Bladder Map template ([Appendix 11](#)) should be used to document the approximate size and location of any abnormalities, as well as the approximate location of any biopsies performed. For all patients, additional evaluation (imaging, exam under anesthesia, biopsies) should be obtained as clinical indicated or if progression is suspected, performed at investigator discretion for any of the following circumstances:
- Abnormal cystoscopy
 - Positive urine cytology
 - Two sequential suspicious/indeterminate urine cytology specimens
- ^z Patients with recurrent low-grade papillary disease will be required to undergo resection with TURBT (unless medically contraindicated) and may continue in the study and receive study treatment. Patients with persistent and/or recurrent high-grade NMIBC without progression at 12 weeks may continue in the study provided there is no evidence of progression to muscle invasive disease. Patients with persistent and/or recurrent high-grade NMIBC at the 6-month assessment will be discontinued from study therapy. Patients with progression to muscle invasion at any time will be discontinued from study therapy.
- ^{aa} Health-related quality of life will be assessed using the EORTC QLQ-C30 and EORTC QLQ-NMIBC24.

Appendix 2

Schedule of Assessments: Cohorts 1b, 2, and 3 (cont.)

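### For Cohort 1A only, Appendix 1 puts off-treatment tumor assessments 6 months apart with no anchor date, against 12 weeks elsewhere, so recurrence can be dated later and the 6-month CR visit can be missed

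*Combined protocol and SAP*

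**What the plan says.** **Schedule for all cohorts.** Section 3.1.2, which covers every cohort, states: "Tumor response assessment via cystoscopy and urine cytology will occur every 12 weeks for the first 2 years, and every 24 weeks thereafter". Section 4.5.5 follows guidelines that "recommend cystoscopic examination and urine cytology every 12 weeks for the first 2 years". For Cohort 1A, Appendix 1 footnote x says the same: "Tumor response assessment will occur every 12 weeks for the first 2 years, and every 24 weeks thereafter".

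**After stopping treatment without recurrence, progression or cystectomy.** Under Section 3.1.2 these patients "will continue to undergo tumor assessments per protocol until they experience disease recurrence/progression or cystectomy". Under Section 4.5.11 they "will continue to undergo tumor assessments per study protocol, until they experience disease recurrence/progression or cystectomy". Appendix 1 footnote y, attached to the Follow-Up cell of the tumor assessment row for Cohort 1A, says instead that they "will continue to undergo tumor assessments every 6 months until they experience disease recurrence/progression or cystectomy". It does not say whether the 6 months run from Cycle 1 Day 1 (C1D1), from the last assessment or from the discontinuation visit.

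**Other cohorts.** In Appendix 2 the matching Follow-Up cell carries footnote z, which begins "Patients with recurrent low-grade papillary disease will be required to undergo resection with TURBT" and goes on to who may stay on treatment. It gives no off-treatment interval.

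**Endpoints that depend on these visits.** The primary endpoint is "CR at the 6-month evaluations after the start of study treatment". RFS is reported at 6, 12 and 18 months. Duration of CR ends at recurrence or death and is otherwise censored when the patient was last known to be alive and recurrence free (Section 6.4.2).

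**The concern.** A recurrence found at a scheduled visit is dated no earlier than that visit. If one cohort is seen less often after stopping treatment, its recurrences tend to be dated later, and its duration of CR and RFS can look longer for reasons unrelated to the drug. Cohort 1A is the monotherapy group, and its results will be read beside those of the BCG combination cohorts, so a difference in visit spacing found only there is unwelcome.

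The second risk is to the primary endpoint. A patient who stops for toxicity in the first months, with no recurrence, still belongs to the analysis, because Section 6 includes everyone treated. If the next scheduled assessment falls well after Week 24, there may be no 6-month CR reading. Section 6.4.1 does not say how such a patient is counted. With about 12 patients in Cohort 1A, one patient matters.

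**Working it through.** **1. The plan's own precision.** Clopper-Pearson limits for 5 responders of 12 are the 2.5% quantile of Beta(5, 8) and the 97.5% quantile of Beta(6, 7). These are 15.2% and 72.3%, which reproduce the Table 11 entry of 42% (15%, 72%). The other rows of Tables 11 and 12 also reproduce. The plan's figures are not in dispute; this row serves as a yardstick.

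**2. Where the next visit falls.** Six months is 26.1 weeks. The discontinuation visit comes within 30 days of the last dose, that is up to 30/7 = 4.3 weeks later, and it includes a tumor assessment. The next assessment under footnote y, in study weeks, is then:

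| Last dose | Discontinuation visit | Counted from that visit (+26.1) | Counted from a Week 12 assessment | Counted from C1D1 |
|---|---|---|---|---|
| Week 3 | 3 to 7.3 | 29.1 to 33.4 | none yet | 26.1 |
| Week 9 | 9 to 13.3 | 35.1 to 39.4 | 38.1 if done | 26.1 |
| Week 18 | 18 to 22.3 | 44.1 to 48.4 | 38.1 | 26.1 |

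Counted from the discontinuation visit or from Week 12, the next assessment falls after Week 24. The 6-month reading is then lost unless the discontinuation visit itself lies close to Week 24, as it can for a last dose at Week 18. Counted from C1D1, the visit is near Week 26 and the endpoint is kept.

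**3. Later dating of recurrence.** The longest scheduled gap rises from about 12 weeks to about 26. As an illustration, take a last dose at Week 9, a discontinuation visit at Week 13.3, the 6 months counted from that visit, and recurrence equally likely at any time afterwards.
- Assessments up to Week 104, counting the discontinuation visit, fall from 8 to 4.
- Mean delay from recurrence to the next visit rises from 6.1 to 14.0 weeks.
- Month 12 (Week 52): on the 12-week schedule the last earlier visit is Week 48, so (52 - 48)/(52 - 13.3) = 10% of recurrences by then are not yet dated. Under footnote y it is Week 39.4, giving (52 - 39.4)/(52 - 13.3) = 33%.
- Month 18 (Week 78): the same calculation gives 9% and 19%.

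The effect depends strongly on when the patient stops. For a last dose at Week 15 the Month 12 shares are 12% and 20%. For a last dose at Week 24 they are 17% and 100%, because the first visit under footnote y falls after Week 52. After 2 years the intervals are 24 weeks and 6 months, which is no material difference.

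**4. How many patients.** The documents give no expected number. As an assumption, the Table 3 rates of withdrawal from treatment for adverse events are 5.9%, 2.9% and 4.2%. Multiplied by 12 they give 0.71, 0.35 and 0.50 patients. Section 1.3.4 gives seven events behind the 5.9%, and four of them (cardiac arrest, myocardial infarction, sepsis, respiratory failure) also appear as Grade 5 events. If these were the same patients, 3/119 = 2.5% remain, or 0.30 of 12.

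**5. What one patient does to the CR rate.** Losing one true responder moves 5/12 = 41.7% to 4/12 = 33.3% (9.9% to 65.1%), a fall of 1/12 = 8.3 points. If the patient is excluded, the result is 4/11 = 36.4% (10.9% to 69.2%). If the patient is counted as a non-responder and was one, nothing changes.

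**The case against.** The strongest reply is that the primary endpoint is already protected. Section 3.1.2 requires a biopsy from every patient 6 months after C1D1 whether or not treatment continues, Section 4.5.5 makes biopsies mandatory at the 6-month assessment, and Appendix 1 footnote w repeats the requirement for all patients. A reader might infer from footnote y that early stoppers in Cohort 1A have no 6-month reading by design. The documents do not support that. What remains is narrower: footnote w ties the biopsy to the time before Cycle 9, which an early stopper never reaches, and the Appendix 1 grid lists it only under Weeks 1–96, with only the optional biopsy under Follow-Up. A site working from the grid could miss it.

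It can also be said that Section 4.5.11 opens by referring to the appendices for follow-up, so that continuing per protocol may include footnote y, and that Section 4.5 cites guidelines allowing 3 to 6 months. Both are fair. On that reading, however, Cohort 1A still differs from the other cohorts without a stated reason, and footnote y still departs from the all-cohort 12-week schedule.

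Late dating is also limited. Section 4.5.5 lets cystoscopy and cytology be repeated whenever recurrence is suspected, and allows the date of a positive cytology to serve as the recurrence date once recurrence is shown. This helps for suspected recurrence, less for silent recurrence. A reader might infer that duration of CR and RFS for Cohort 1A as a whole are materially lengthened. With so few patients likely to be involved, and only descriptive analyses by cohort, that does not follow.

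**Conclusion.** The inconsistency is real and confined to Cohort 1A. Footnote y disagrees with the all-cohort schedule and with footnote x beside it, has no counterpart in Appendix 2, and lacks an anchor date. It has consequences only in the first 2 years.

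For an affected patient, the longest gap between scheduled assessments goes from about 12 to about 26 weeks, and recurrence can be dated correspondingly later than in the other cohorts. Loss of the 6-month CR reading is possible but not certain. It requires that the 6 months be counted from the discontinuation visit or a Week 12 assessment, that the discontinuation visit not fall near Week 24, and that the site not apply the 6-month biopsy off treatment.

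The number affected is probably below one of 12. That figure borrows rates from metastatic disease, where median treatment lasted 12 to 15 weeks in the two IMvigor210 cohorts. Treatment here can last 96 weeks, and patients may stop for reasons other than adverse events, so the true number could be higher. On the other hand, some of those withdrawals appear to be deaths, and only stops before about Week 24 threaten the primary endpoint. The mean delays and undated shares assume recurrence uniform in time and counting from the discontinuation visit. The 8.3 points apply only if the unassessed patient was a true responder.

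This is a small effect, but an avoidable one, and it should be corrected.

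**What to change.** Reconcile Appendix 1 footnote y with Sections 3.1.2, 4.5.5 and 4.5.11 so that one off-treatment assessment interval applies in every cohort, counted from C1D1 because the 6-month CR and the RFS landmarks are timed from the start of treatment. State the same rule in Appendix 2, where the Follow-Up cell now gives no interval.

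In the Appendix 1 grid, mark under Follow-Up that the 6-month CR assessment, including the biopsy already required of all patients, also applies to those off treatment and still followed. Word footnote w by time from C1D1 as well as by Cycle 9.

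The cost is a footnote and a grid entry. If the footnote is aligned with the body, no patient has an assessment that the body does not already require; extra cystoscopies arise only where sites have been following the footnote.
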